#### 3.29i Active CNS metastasis.

NOTE: Patients with prior brain metastases that are asymptomatic without corticosteroid use and stable or improved  $\geq 90$  days after treatment with surgery or radiation are not excluded.

3.29j Receipt of a live vaccine  $\leq$  30 days prior to registration.

#### 4.0 Study Schedules

#### 4.1 Test schedule for Melanoma

	≤14 days prior to	After	Cycle 1	Cycles	At completion of	End of
Tests and Procedures 	Registration	Reg	Day 1	2-3	each cycle (Cycle 3+)	Тх
window			$\pm 1 \text{ day}$	$\pm 3 \text{ days}$	$\pm 3 \text{ days}^2$	$\pm 7 \text{ days}$
Physical exam, weight, ECOG performance status	Х		Х	Х	Х	Х
Height	Х					
Serum pregnancy test	X 					
Hematology (WBC with differential, Hgb, PLT)	Х		X4		Х	Х
Chemistry profile (creatinine, AST, ALT, alkaline phosphatase, T bili, direct bilirubin, sodium, potassium, random glucose)	Х				Х	Х
Thyroid function cascade (TSH, reflex per Mayo standard if abnormal)	Х			Х	Х	Х
LDH	Х				Х	Х
Coagulation (INR)	Х			X 	$X^6$	
Adverse event assessment	Х				Х	Х
Radiologic evaluations (CT scan, PET/CT, or MRI)	X 				$X^8$	Х
Venous Access Assessment	X 					
Apheresis			Х			
Research blood for immune monitoring R (See Section 14.0) 		Х		X 	Х	Х
Research specimen submission: Tumor biopsies R (See Section 17.0)				X 	X 	

<sup>1 Cycle = 21 days; All tests and procedures are as clinically indicated, unless noted with an R to indicate funding by research. Hematology, chemistry profile, thyroid function cascade, coagulation tests, and imaging may be performed more frequently at physician discretion.

 Coagulation tests should be repeated at the completion of Cycles 1, 2, and 4. If treatment is delayed, coagulation tests should be repeated ≤48 hours prior to tumor biopsy.

 Coagulation tests should be repeated at the completion of Cycles 1, 2, and 4. If treatment is delayed, coagulation tests should be repeated ≤48 hours prior to tumor biopsy.

 Baseline radiology  $\leq 28$  days prior to registration

 Assessment of venous access must be done  $\geq$ 3 days prior to apheresis.

<sup>2 Window of 3 days applies to Cycles 2-5. After Cycle 5, window is  $\pm$ 7 days.

<sup>3 For persons of childbearing potential only. Must be done  $\leq$ 7 days prior to registration.

<sup>4 Repeat hematology tests on Cycle 1, Day 1 only if most recent tests were performed >7 days prior to Cycle 1, Day 1.

<sup>8 Imaging is performed at the end of Cycle 4 and then at the end of every fourth cycle of treatment (end of Cycle 8, 12, 16, etc.). Exception: if a patient has PD yet continues protocol treatment, the next imaging should take place two cycles after the imaging showing PD. If that patient continues on protocol treatment, imaging should then take place every 4 cycles.

<sup>10 Blood draw for immune monitoring will be collected prior to the start of Cycles 1-5 and prior to the start of each post-imaging cycle thereafter (prior to Cycle 9, 13, 17, etc.)

<sup>11 In addition to the research blood collection on Day 1, research blood will be collected as per Section 14 on Cycle 2, Days 2-5. The collection on Cycle 2, Day 2 should take place 2-4 hours after completion of cryoablation and mDC therapy.

<sup>12 Tumor biopsies will be performed immediately prior to cryoablation on Cycle 2 Day 1 or 2 and Cycle 3 Day 1 or 2

<sup>13 Tumor biopsies will be performed at the end of Cycle 4 after radiologic evaluation

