#### 6.6 Treatment start

Treatment cannot begin prior to registration and must begin ≤7 days after registration.

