#### 7.0 **Protocol Treatment**

Use actual weight or estimated dry weight if fluid retention.

Cycle length is 21 days with the exception of Cycle 1 which may be extended an additional 7 days to allow for dendritic cell production.

Dose-limiting toxicity (DLT) is defined as one of the following events occurring during the first two cycles of protocol therapy and attributed as possibly, probably, or definitely related to protocol therapy.

- Any Grade 3+ toxicity
- Grade 2 infusion reaction, acute or chronic kidney disease, or pneumonitis that does not resolve to Grade 0-1 within 3 weeks.

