## 7.2 Run-in Phase Ib

7.21 Schedule 1 (6 patients):

Cycle 1, Day 1: Apheresis (see Section 7.3) and pembrolizumab 200mg IV

Cycles 2 and 3, Day 1: Pembrolizumab 200mg IV

Cycles 2 and 3, either Day 1 or Day 2: cryoablation, injection of  $30-60 \times 10^6$  mDCs, and injection of 0.5 ml Prevnar13, per Section 7.4

Cycle 4 Day 1 and all subsequent cycles: pembrolizumab 200mg IV

If at most one of the 6 patients enrolled onto Schedule 1 develops a DLT during the first 3 cycles of treatment then Schedule 1 will be carried forward to the continuation phase.

7.22 Schedule -1:

If two or more patients enrolled onto Schedule 1 develop a DLT during the first 3 cycles of treatment, then an additional 6 patients will be treated as follows:

Cycle 1, Day 1: Apheresis and pembrolizumab 200mg IV

Cycles 2 and 3, either Day 1 or Day 2: Cryoablation, injection of  $30-60 \times 10^6$  mDCs, and injection of 0.5 ml Prevnar13, per Section 7.5. Note: No pembrolizumab will be given in Cycles 2 and 3 on this schedule.

Note: No pembrolizumab will be given in Cycles 2 and 3 on this schedul

Cycle 4 Day 1 and all subsequent cycles: pembrolizumab 200mg IV

- If at most one of the 6 patients enrolled onto Schedule -1 develops a DLT during the first 3 cycles of treatment then Schedule -1 will be carried forward to the continuation phase.
- If two or more of the patients enrolled onto Schedule -1 develop a DLT during the first 3 cycles of treatment, enrollment will be discontinued for the study team to review the safety data and consider amending the protocol.

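### As printed, table 4.1 schedules no chemistry from baseline to completion of Cycle 3, and no hematology after Cycle 1 Day 1 until then, so the two-cycle DLT window contains no planned post-treatment panel

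*Combined protocol and SAP*

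**What the plan says.** **Table 4.1.**
- Chemistry is marked at baseline, in the completion column ("each cycle (Cycle 3", then a plus sign) and at End of Tx.
- Hematology has the same marks plus Cycle 1 Day 1, where footnote 4 says: "Repeat hematology tests on Cycle 1, Day 1 only if most recent tests were performed >7 days prior to Cycle 1, Day 1".
- Under Cycles 2-3 the chemistry, hematology and adverse event rows are blank. Physical exam, thyroid function, INR, research blood and biopsy are marked there.
- Footnote 1: "Hematology, chemistry profile, thyroid function cascade, coagulation tests, and imaging may be performed more frequently at physician discretion".
- Footnote 2, attached to the completion column: "Window of 3 days applies to Cycles 2-5".
- Footnotes 5 and 6 place INR at completion of Cycles 1, 2 and 4, and add: "If treatment is delayed, coagulation tests should be repeated ≤48 hours prior to tumor biopsy".

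**Rules that use laboratory grades.**
- Section 7.0 counts "Any Grade 3+ toxicity" as a DLT in the first two cycles if related to treatment, and also Grade 2 kidney events that do not resolve within 3 weeks.
- Section 16.1 limits DLTs to infusion reactions, kidney events and pneumonitis, also over two cycles.
- Sections 7.2 and 16.11 choose the schedule from DLTs over three cycles.
- Table 8.21 holds treatment for Grade 2 kidney events and for other Grade 3 non-hematologic events.
- Section 16.13 acts on related Grade 4 hematologic and Grade 3 or worse non-hematologic toxicity.

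**Other text on monitoring.**
- Section 8.1 requires an adverse event check before each pembrolizumab dose.
- Section 10.61 has creatinine, ALT, AST, bilirubin and anemia graded at each evaluation.
- Section 7.5 requires a hematologic assessment before discharge after solid-organ ablation.
- Sections 15.194 and 15.199d ask for close monitoring of liver tests and blood counts, without dates.
- On Schedule -1: "No pembrolizumab will be given in Cycles 2 and 3 on this schedule".

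**The concern.** The run-in selects the Phase II schedule from six patients and tolerates at most one DLT, so a single unrecorded event can change the choice. Symptomatic events should surface at the scheduled exams. Asymptomatic laboratory toxicity surfaces only if blood is drawn.

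Without a scheduled draw in the two-cycle window, such an event may be missed, or found too late to be dated to that window. Patients of clinicians who test often would be more likely to be counted than patients of those who do not. The Grade 2 kidney criterion is especially exposed, because it needs both a first abnormal value and a repeat within three weeks. The per-10-patient DLT check in 16.5 carries the same weakness into Phase II.

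There is also a procedural point. INR is repeated before the Cycle 2 and Cycle 3 biopsies and cryoablations, but a platelet count is not.

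**Working it through.** The plan gives no figure of its own here, so the check is a reading of the table plus calendar arithmetic in nominal days.

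**Inputs.** A cycle lasts 21 days, and Cycle 1 may last 28 (7.0). Baseline laboratory tests are at most 14 days before registration (3.17, 4.1). On treatment start: "Treatment cannot begin prior to registration and must begin ≤7 days after registration" (6.6). Hematology is at most 7 days old at Cycle 1 Day 1 (footnote 4). The visit window at completion of Cycle 3 is plus or minus 3 days.

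**Step 1: is the blank a column shift in the extracted table?** Exam, thyroid, INR, research blood and biopsy all carry marks under Cycles 2-3, and column positions agree across rows. A shift is unlikely.

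**Step 2: heading read as printed.**
- End of the two-cycle window: 21 + 21 = 42 days, or 28 + 21 = 49.
- Completion of Cycle 3: 42 + 21 = 63 days, or 49 + 21 = 70.
- Age of baseline chemistry at Cycle 1 Day 1: 0 to 14 + 7 = 21 days.
- Interval between consecutive scheduled chemistry panels: 63 + 0 = 63 to 70 + 21 = 91 days, or 94 with the 3-day window.
- The same interval for hematology: 63 + 0 = 63 to 70 + 7 = 77 days, or 80 with the window.
- Age of the latest *scheduled* chemistry: at Cycle 2 Day 1, 21 + 0 = 21 to 28 + 21 = 49 days; at Cycle 3 Day 1, 42 + 0 = 42 to 49 + 21 = 70 days.
- Age of the latest *scheduled* platelet count: 21 to 28 + 7 = 35 days, and 42 to 49 + 7 = 56 days. The second is shorter if a solid organ was ablated in Cycle 2.

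**Step 3: scheduled post-treatment panels under each reading** (a draw at the close of a window counts as inside it).

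| Reading of the completion column | Two-cycle window | Three-cycle window |
|---|---|---|
| From completion of Cycle 3 (as printed) | 0 | 1 |
| From completion of Cycle 2 | 1 | 2 |
| From completion of Cycle 1 | 2 | 3 |
| As printed, with Cycles 2-3 cells marked | 2 | 3 |

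Under the second reading, chemistry is still not scheduled before the first cryoablation and mDC injection, in Cycle 2.

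**Step 4: which rules need which test.**

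| Rule | Chemistry | Hematology |
|---|---|---|
| 7.0 DLT | yes | yes |
| 16.1 DLT | yes (kidney only) | no |
| Table 8.21 holds | yes | no (no hematologic row) |
| 16.13 stopping rule | yes | yes |

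**The case against.** Three arguments carry weight.

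1. **The heading may be a slip.** Footnote 2 speaks of Cycles 2-5, and footnote 6, attached to the same column, names completion of Cycles 1, 2 and 4. If the column was meant to start at completion of Cycle 1, the gap disappears. This stands as a possibility but is not conclusive. Footnote 2 concerns only the visit window. Footnote 6 concerns only INR and repeats footnote 5, which is attached to the INR mark under Cycles 2-3. That column can therefore equally be read as the end-of-Cycle-1 and end-of-Cycle-2 visits, in which case the blanks are real.

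2. **Other text calls for the tests.** Section 8.1 requires an evaluation before each pembrolizumab dose, and 10.61 grades creatinine, ALT, AST and bilirubin at each evaluation. Those grades need a blood sample. Footnote 1 permits extra testing and 15.19 urges it. A reader might infer that the hold decisions before doses 2 and 3 would rest on baseline chemistry. The documents do not support that for Schedule 1, because 8.1 and 10.61 together imply current laboratory grades. What remains is that none of these sections schedules a draw. On Schedule -1, with no pembrolizumab in Cycles 2 and 3, the 8.1 check does not apply in those cycles. The exam, the 10.61 grading and the 2-hour post-procedure monitoring still do.

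3. **Hematology matters less than chemistry.** This stands in full: blood counts bear only on 7.0 and 16.13, plus platelets before the procedures.

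**Conclusion.** The point holds for table 4.1 as printed: 0 scheduled post-treatment panels in the two-cycle DLT window, 1 at the close of the three-cycle window, and 63 days (70 if Cycle 1 is extended) from Cycle 1 Day 1 to the first scheduled panel. The exceptions are End of Tx tests in patients who stop early and the hematologic assessment after solid-organ ablation. The result depends on the literal heading, and only a start at completion of Cycle 1 would close the gap.

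A reader might go further and infer that a known share of silent toxicity would be missed. The documents give neither the frequency nor the duration of such events, so no share can be stated. Toxicity still present at the end of Cycle 3 would be found then. Discretionary testing may also be common in practice. The supportable conclusion is that laboratory ascertainment in the run-in is left to discretion when it should be scheduled. The primary endpoint, the sample size and the response analysis are unaffected. The change should be made for safety and for consistent DLT counting.

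**What to change.** - In table 4.1, mark hematology, chemistry and AE assessment under Cycles 2-3, with results reviewed before that day's treatment. The longest planned on-treatment interval then falls from 63-70 days to 21-28 days, and platelets are available before both biopsies and cryoablations.
- Reword 8.1 so that the adverse event check takes place at the start of every cycle, whether or not pembrolizumab is given. Schedule -1 needs this.
- Correct or confirm the Cycle 3 onward heading in light of footnotes 2 and 6. If an earlier start was intended, state that one draw serves both the completion visit and the next cycle's pre-treatment check.

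Cost: three table cells, one sentence and a heading check, plus up to two routine blood panels per patient (before Cycles 2 and 3) at visits where thyroid, INR and research blood are already drawn.

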# 4.2 Event Monitoring/Survival Follow-up

	Event Monitoring Phase 					
	q. 3 months After PD					
	until PD	At PD	q. 6 months	Death	New Primary	
Event Monitoring	X	Х	Х	X	At each occurrence	

1. If a patient is still alive 5 years after registration, no further follow-up is required.

# 5.0 Grouping Factor

Cohort: Run-in Phase Ib Dose level 1 vs. Run-in Phase Ib Dose level -1 vs. Continuation Phase (Phase II)

#### 6.0 **Registration Procedures**

Prior to discussing protocol entry with the patient, call the Mayo Clinic Cancer Center Registration Office [contact]) to confirm study status and insure that a place on the protocol is currently available to the patient

## 6.1 Registering a patient

To register a patient, access the Mayo Clinic Cancer Center (MCCC) web page and enter the remote registration/randomization application. The registration/randomization application is available 24 hours a day, 7 days a week. Back up and/or system support contact information is available on the Web site. If unable to access the Web site, call the MCCC Registration Office at [contact] between the hours of 8 a.m. and 4:30 p.m. Central Time (Monday through Friday).

The instructions for the registration/randomization application are available on the MCCC web page (http://hsrwww.mayo.edu/ccs/training) and detail the process for completing and confirming patient registration. Prior to initiation of protocol treatment, this process must be completed in its entirety and a MCCC subject ID number must be available as noted in the instructions. It is the responsibility of the individual and institution registering the patient to confirm the process has been successfully completed prior to release of the study agent. Patient registration via the registration/randomization application can be confirmed in any of the following ways:

- Contact the MCCC Registration Office [contact]. If the patient was fully registered, the MCCC Registration Office staff can access the information from the centralized database and confirm the registration.
- Refer to "Instructions for Remote Registration" in section "Finding/Displaying Information about A Registered Subject."

# 6.2 Verification

Prior to accepting the registration, registration/randomization application will verify the following:

- IRB approval at the registering institution
- Patient eligibility
- Existence of a signed consent form
- Existence of a signed authorization for use and disclosure of protected health information

# 6.3 Documentation of IRB approval

Documentation of IRB approval must be on file in the Registration Office before an investigator may register any patients.

In addition to submitting initial IRB approval documents, ongoing IRB approval documentation must be on file (no less than annually) at the Registration Office ([contact]). If the necessary documentation is not submitted in advance of attempting patient registration, the registration will not be accepted and the patient may not be enrolled in the protocol until the situation is resolved.

When the study has been permanently closed to patient enrollment, submission of annual IRB approvals to the Registration Office is no longer necessary.

# 6.4 Correlative studies

A mandatory translational research component is part of this study; the patient will be automatically registered onto this component (Sections 3.19b, 14.0, 17.0).

At the time of registration, the following will be recorded:

- Patient has/has not given permission to store and use his/her sample(s) for future research of cancer at Mayo.
- Patient has/has not given permission to store and use his/her sample(s) for future research to learn, prevent, or treat other health problems.
- Patient has/has not given permission for MCCC to give his/her sample(s) to researchers at other institutions.

#### 6.5 Treatment on protocol

Treatment on this protocol must commence at Mayo Clinic in Rochester, Minnesota under the supervision of a medical oncologist.

#### 6.6 Treatment start

Treatment cannot begin prior to registration and must begin ≤7 days after registration.

#### 6.7 Pretreatment

Pretreatment tests/procedures (see Section 4.0) must be completed within the guidelines specified on the test schedule.

# 6.8 **Baseline symptoms**

All required baseline symptoms (see Section 10.6) must be documented and graded.

## 6.9a Study Conduct

The clinical trial will be conducted in compliance with regulations (21 CFR 312, 50, and 56), guidelines for Good Clinical Practice (ICH Guidance E6), and in accordance with general ethical principles outlined in the Declaration of Helsinki; informed consent will be obtained from all participating patients; the protocol and any amendments will be subject to approval by the designated IRB prior to implementation, in accordance with 21 CFR 56.103(a); and subject records will be stored in a secure location and subject confidentiality will be maintained. The investigator will be thoroughly familiar with the appropriate use of the study drug as described in the protocol and Investigator's Brochure. Essential clinical documents will be maintained to demonstrate the validity of the study and the integrity of the data collected. Master files should be established at the beginning of the study, maintained for the duration of the study and retained according to the appropriate regulations.

#### 7.0 **Protocol Treatment**

Use actual weight or estimated dry weight if fluid retention.

Cycle length is 21 days with the exception of Cycle 1 which may be extended an additional 7 days to allow for dendritic cell production.

Dose-limiting toxicity (DLT) is defined as one of the following events occurring during the first two cycles of protocol therapy and attributed as possibly, probably, or definitely related to protocol therapy.

- Any Grade 3+ toxicity
- Grade 2 infusion reaction, acute or chronic kidney disease, or pneumonitis that does not resolve to Grade 0-1 within 3 weeks.

## 7.1 Drugs used in this study

Pembrolizumab at FDA approved dose for metastatic melanoma of 200mg IV every 21 days

Autologous mature dendritic cells (mDCs) injected into the tumor site

Prevnar13® injected into the tumor site with the DCs

## 7.2 Run-in Phase Ib

7.21 Schedule 1 (6 patients):

Cycle 1, Day 1: Apheresis (see Section 7.3) and pembrolizumab 200mg IV

Cycles 2 and 3, Day 1: Pembrolizumab 200mg IV

Cycles 2 and 3, either Day 1 or Day 2: cryoablation, injection of  $30-60 \times 10^6$  mDCs, and injection of 0.5 ml Prevnar13, per Section 7.4

Cycle 4 Day 1 and all subsequent cycles: pembrolizumab 200mg IV

If at most one of the 6 patients enrolled onto Schedule 1 develops a DLT during the first 3 cycles of treatment then Schedule 1 will be carried forward to the continuation phase.

7.22 Schedule -1:

If two or more patients enrolled onto Schedule 1 develop a DLT during the first 3 cycles of treatment, then an additional 6 patients will be treated as follows:

Cycle 1, Day 1: Apheresis and pembrolizumab 200mg IV

Cycles 2 and 3, either Day 1 or Day 2: Cryoablation, injection of  $30-60 \times 10^6$  mDCs, and injection of 0.5 ml Prevnar13, per Section 7.5. Note: No pembrolizumab will be given in Cycles 2 and 3 on this schedule.

Note: No pembrolizumab will be given in Cycles 2 and 3 on this schedul

Cycle 4 Day 1 and all subsequent cycles: pembrolizumab 200mg IV

- If at most one of the 6 patients enrolled onto Schedule -1 develops a DLT during the first 3 cycles of treatment then Schedule -1 will be carried forward to the continuation phase.
- If two or more of the patients enrolled onto Schedule -1 develop a DLT during the first 3 cycles of treatment, enrollment will be discontinued for the study team to review the safety data and consider amending the protocol.

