# 7.4 Apheresis

Patients will undergo apheresis on Cycle 1, Day 1, from which monocytes will be collected by immunomagnetic isolation and cultured *in vitro* under GMP conditions to generate mature DCs (mDCs). The generated mDCs will be frozen and stored until ready for use. Autologous mature dendritic cells (mDCs) will be prepared for administration into the cryoablated tumor. At a minimum, mDCs necessary for 2 injections (30-60  $\times 10^6$  per injection) will be manufactured. Additional mDCs and lysate will be stored for potential retreatment and immune monitoring assays. If insufficient mDCs are available for treatment, the total mDCs should be split into two doses, and the treating physician may determine whether to continue with protocol treatment or take the patient off study.

NOTE: If first mDC production attempt does not yield any releasable mDCs, then one additional apheresis may be attempted.

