# 7.5 Cryoablation, mDC administration, and Prevnar13 administration

Each patient will undergo percutaneous cryoablation within 36 hours of pembrolizumab treatment on Cycles 2 and 3. (Generally, this will take place on Cycle 2, Day 2, and Cycle 3, Day 2. However, it is acceptable that cryoablation could be performed on Cycle 2, Day 1, and Cycle 3, Day 1.) Two distinct metastatic lesions will be treated with cryoablation, one during Cycle 2, and the other during Cycle 3. Our general cryoablation technique has been previously described (McMenomy et al. JVIR 2013; 24:207-213). Due to the extended length of the procedure, requiring the patient to lie still (expected duration 45 minutes), sedation will be managed by the Department of Anesthesia. Using ultrasound and/or CT guidance, a cryoprobe will be placed in the index melanoma lesion. Research biopsies (6 18-gauge cores) will be obtained immediately prior to freezing the tumor. The lesion will be treated using a conventional freeze-thaw- freeze cycle with the endpoint being the generation of an iceball that measures at least 75% of the diameter of the index tumor but may encompass the entire tumor with a margin of normal tissue.

Following the freezing procedure, the cryoprobe will be actively warmed and then withdrawn. After the lesion has thawed, a 22 G needle will be placed under ultrasound or CT-guidance into the ablated portion of the lesion. The mDC will be administered through this needle over different areas of the cryoablated region and then flushed with 1ml of sterile saline. Prevnar13® will be injected into the ablated portion of the lesion after administration of mDCs. The patient will be transferred to the recovery area and monitored for 2 hours following cryoablation and DC injections for acute toxicity. Given the elevated risk of solid organ cryoablation, patients undergoing ablation of such tumors will be admitted to the hospital for overnight observation, including hematologic assessment prior to discharge.

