16.11 Run-in phase (Phase Ib)

Six patients will be enrolled onto Schedule 1. If at most one of these 6 patients develops a DLT during the first 3 cycles of treatment then Schedule 1 will be carried forward to the continuation phase (Phase II).

If two or more patients enrolled onto Schedule 1 develop a DLT during the first 3 cycles of treatment, then an additional 6 patients will be treated on Schedule -1 (See Section 7.2).

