16.32 Feasibility

A point estimate of the proportion of patients who received both intra-tumoral DC injections among those who initiated treatment will be determined. A 95% exact binomial confidence interval for this proportion will be constructed.

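### The run-in decision counts DLTs among six enrolled patients with no exposure requirement, which tilts it toward carrying the schedule forward

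*Combined protocol and SAP*

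**What the plan says.** The run-in treats six patients on Schedule 1. Section 7.2 states the condition for carrying it forward: "If at most one of the 6 patients enrolled onto Schedule 1 develops a DLT during the first 3 cycles of treatment". Section 16.11 opens with "Six patients will be enrolled onto Schedule 1" and continues "If at most one of these 6 patients develops a DLT during the first 3 cycles of treatment". Section 7.22 applies the same threshold to six patients on Schedule -1.

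On both schedules Cycle 1 consists of apheresis and pembrolizumab. The local treatment comes later. Section 7.5 says "Each patient will undergo percutaneous cryoablation within 36 hours of pembrolizumab treatment on Cycles 2 and 3", and the mDC and Prevnar13 injections follow each ablation.

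The plan foresees that some patients may not get that far. Section 7.4 provides that "If first mDC production attempt does not yield any releasable mDCs, then one additional apheresis may be attempted". If cells are too few, the supply is to be divided into two doses, and "the treating physician may determine whether to continue with protocol treatment or take the patient off study". Section 16.32 makes receipt a feasibility outcome: "A point estimate of the proportion of patients who received both intra-tumoral DC injections among those who initiated treatment will be determined". No expected rate of non-receipt is given.

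The DLT definition in 7.0, like the one in 16.1, covers events "occurring during the first two cycles of protocol therapy", whereas the decision rules in 7.2 and 16.11 count over three cycles.

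**The concern.** Pembrolizumab is given at its approved dose (7.1), so what the run-in tests is the addition of cryoablation, mDCs and Prevnar13. A patient who leaves after Cycle 1 carries no information about that addition, yet takes one of the six places. The allowance of one DLT stays fixed while the number of patients who could show a DLT from the full regimen falls to five or four. The schedule then passes more easily than a six-patient rule is meant to allow, and every later patient is treated on the strength of that decision.

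**Working it through.** **The plan's own figures.** No operating characteristics are stated for the run-in. The stated phase II design does reproduce. With 33 patients and rejection at 7 or more responses, the exact binomial test has one-sided level 0.0930 at a 12% response rate (limit 0.10) and power 0.9056 at 30% (stated 90%).

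**Does another clause remove or replace an unexposed patient?**
- Sections 13.5 (withdrawn) and 13.8 (cancel) apply only before any study treatment. This patient has already had pembrolizumab.
- Section 13.7 (major violation) concerns Cycle 1 treatment and evaluability for the primary endpoint.
- Section 16.31 makes every eligible patient who started treatment evaluable for safety, which points toward counting the patient.
- Sections 16.13 and 16.5 set no exposure condition.

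None of them does.

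**Size of the effect.** From the plan: six patients, pass on 0 or 1 DLT. Assumed, because the documents give no values:
- p, the true DLT probability in an exposed patient: 30% or 40%
- b, the DLT probability from pembrolizumab or apheresis alone: 0 or 10%
- k, the number unexposed among the six: 0, 1 or 2

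With m = 6 − k exposed,

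P(carry forward) = (1−p)^m (1−b)^k + m p (1−p)^(m−1) (1−b)^k + k b (1−b)^(k−1) (1−p)^m.

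Example, p = 0.30:
- k = 0: 0.7^6 + 6(0.3)(0.7^5) = 0.1176 + 0.3025 = 0.420
- k = 1, b = 0: 0.7^5 + 5(0.3)(0.7^4) = 0.1681 + 0.3602 = 0.528
- k = 1, b = 0.10: 0.9(0.1681) + 0.9(0.3602) + 0.1(0.1681) = 0.1513 + 0.3241 + 0.0168 = 0.492

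| True DLT rate | Background risk | 0 unexposed | 1 unexposed | 2 unexposed |
|---|---|---|---|---|
| 30% | 0 | 0.42 | 0.53 | 0.65 |
| 30% | 10% | 0.42 | 0.49 | 0.57 |
| 40% | 0 | 0.23 | 0.34 | 0.48 |
| 40% | 10% | 0.23 | 0.31 | 0.41 |

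**How often it would arise.** Let q be the chance that a patient is never exposed, assumed between 5% and 20%. At least one of six is then unexposed with probability 1 − (1−q)^6:
- q = 5%: 1 − 0.95^6 = 0.26
- q = 20%: 1 − 0.80^6 = 0.74

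Averaging the carry-forward probability over k ~ Binomial(6, q), with p = 40% and b = 0, gives 0.266 at q = 5% and 0.378 at q = 20%, against 0.233 with full exposure.

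**The case against.** Five things can be said for the plan.

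1. A reader might infer that an unexposed patient automatically counts as free of DLT. The documents do not support that. A DLT is an event at least possibly related to protocol therapy, and Cycle 1 already includes pembrolizumab and apheresis, so such a patient can contribute one. This stands, and it is why the results with background risk are shown. The bias becomes smaller but keeps its direction while background risk is below full-regimen risk.

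2. A reader might also infer that trouble with mDC production means leaving the study. Section 7.4 offers another apheresis when no cells are releasable, and divided doses when cells are too few. A patient given divided doses is exposed. Both provisions lower the number unexposed. Neither excludes it, because the second apheresis can fail and the physician may still take the patient off study.

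3. The plan never says that an unexposed patient has tolerated the schedule, so this could be called plain silence. But the stated denominator is enrolment, and nothing removes the patient from it. Followed literally, the rule produces the bias.

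4. Section 16.13 suspends enrolment at any treatment-related death, if 2 or more of the first 6 patients have a qualifying toxicity, or later if 25% or more do. Section 16.5 suspends at 3 or more DLTs in a cohort of 10. These checks limit later harm. They do not correct the run-in decision.

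5. With low non-receipt the average shift is small: about 3 percentage points at q = 5% and p = 40% (0.266 against 0.233). Even six fully exposed patients pass a 30% schedule 42% of the time. The small run-in is the larger limitation, and the fix leaves it in place.

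**Conclusion.** The concern holds as a bias toward carry-forward, conditional on some run-in patients never reaching cryoablation and mDC injection. With one unexposed patient of six, the chance of passing rises by 7 to 11 points at a true DLT rate of 30% (0.42 to 0.49 or 0.53) and by 8 to 10 points at 40% (0.23 to 0.31 or 0.34; unrounded, 0.233 to 0.311 or 0.337). With two, it rises by 15 to 23 points at 30% and by 18 to 24 points at 40%. The lower end of each range takes a 10% background risk and the upper end none. The DLT rates, the background risk and the number unexposed are all assumptions. If every run-in patient is exposed, the problem does not arise.

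A reader might go further and conclude that the schedule would be declared safe on pembrolizumab-only data, or that the response analysis is compromised. The documents support neither. Exposed patients still drive most of the decision, and the response analysis properly keeps everyone who started treatment at the carried-forward schedule.

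**What to change.** First reconcile the DLT window. It is two cycles in 7.0 and 16.1 and three in 7.2 and 16.11, and evaluability cannot be defined until one window applies throughout.

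Then, in 7.2 (both schedules) and 16.11:
- Base the decision on six DLT-evaluable patients. These are patients who received at least one cryoablation with mDC and Prevnar13 injection and were observed through the DLT window, plus any patient who had a DLT. The threshold of one procedure is a choice, since two are scheduled; the sponsor should state the threshold explicitly.
- Let the next registered patient fill a non-evaluable place, for this decision only.
- Keep every patient who started treatment in the response denominator, as 16.1 already does.

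**Cost.** The enrolment pause after six patients (16.2) lengthens. If three cycles apply, each replacement round takes about 3 × 21 = 63 days, or 70 if Cycle 1 is extended by the 7 days that 7.0 allows. Run-in patients on the carried-forward schedule already belong to the 33, so that cohort and its power do not change. Only if Schedule 1 fails does the maximum of 39 (6 + 33) rise, by the number replaced there. No endpoint or procedure is added.
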